9.2.11 Post-Treatment (PT) Visit - *amended*

This section was changed in Amendment 3, see Section 15.1.2.23.

For all subjects (except those who participate in the iohexol clearance study) who are still on treatment with study drug at the end of study visit, this will be performed by telephone contact within 4 weeks + 5 days after last study drug intake. The following will be performed at the PT Visit:

- Record use of concomitant medication (see Section 8.1)
- Record adverse events (see Section 9.6.1), accounting for the rules of assessment and documentation (see Section 9.6.1.3).

For subjects who signed informed consent for the iohexol clearance sub-study, the PT Visit will be performed as an on-site visit with the following procedures and assessments:

- Record use of concomitant medication (see Section 8.1)
- Obtain samples for iohexol clearance (see Section 9.7.8.1.3)
- Record adverse events (see Section 9.6.1), accounting for the rules of assessment and documentation (see Section 9.6.1.3).

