Study drug administration			X		X						
KDQOL-36, EQ-5D-5L			X				X		X	X	
Physical examination	X	X					X		X	X	
Weight, height, waist and hip circumference ^a	X	X	X	X	X	X	X	X	X	X	
Vital signs ^b	X	X	X	X	X	X	X	X	X	X	
12-lead ECG (local)	X	X	X				X		X	X	
PK blood sample					X ⁿ		X ^o				
Full central laboratory	X	X	X		X	X	X		X	X	
Limited chemistry (central)				X				X			
Urinalysis (central) ^c	X	X	X		X		X			X	
Safety laboratory (local) ^d			X	X	X	X	X	X			
Endpoint assessment ^e				X	X	X	X	X	X	X	
AE assessment ^f	X	X	X	X	X	X	X	X	X	X	X
Pregnancy test ^g		X					X				

Table 9–1 Study 16244: schedule of activities and evaluations - amended**NOTE:**

One month corresponds to 30 days

A time frame of ± 7 days is allowed for Visit 2 (Month 1), and for the Up-titration Visit(s).

A time frame of ± 12 days is allowed for all regular visits from Visit 3 (Month 4) onwards.

Abbreviations: ECG = electrocardiogram; EOS = end of study; EQ-5D-5L = EuroQol Group 5 dimension, 5 level questionnaire; KDQOL = Kidney Disease Quality of Life; PD = premature discontinuation; PT = post-treatment; (S)AE = (serious) adverse event; SD = study drug

- ^a Height, waist and hip circumference to be assessed at Run-in Visit only.
- ^b After resting for at least 5 minutes, 3 measurements to be taken with at least 1-minute interval in a sitting position (all 3 readings within a maximum of 20 minutes).
- ^c At Visit 1, first morning void urine samples to be preferably collected on three consecutive days at the subject's home within 7 days before scheduled visit and before any intake of study drug. At the other visits the 3 consecutive samples can be collected ± 7 days from the visit date.
- ^d Blood samples (for potassium and creatinine) for measurement in the local laboratory may be obtained up to 72 hours before a scheduled visit. Samples to be taken only if the subject is still taking study drug,
- ^e Categorical renal endpoints, $\geq 40\%$ or $\geq 57\%$ decrease in eGFR compared to baseline and an eGFR decrease to less than 15 mL/min/1.73 m², have to be confirmed by at least one additional standardized serum creatinine measurement. This confirmation should be done at least 4 weeks after the initial measurement as an unscheduled assessment.
- ^f AEs related to study procedures occurring after signing the informed consent as well as all other AEs starting after randomization will be documented on the respective eCRF pages.

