9.2.10 End of study (EOS) visit - *amended*

This section was changed in Amendment 3, see Section 15.1.2.22.

The following procedures and assessments will be performed at the EOS Visit:

- The subject completes KDQOL-36 and EQ-5D-5L questionnaires (see Section 9.7.7)
- Record use of concomitant medication (see Section 8.1)
- Collect unused study drug and perform accountability to assess compliance (see Section 7.6)
- Perform physical examination (see Section 9.7.3)
- Record body weight (see Section 9.7.4)
- Record vital signs (see Section 9.7.5)
- Perform 12-lead ECG (see Section 9.7.6)
- Take samples (hematology, HbA_{1c}, chemistry, urinalysis) for central laboratory evaluations (see Section 9.7.2.1)
- Optional: if the subject had signed informed consent for the sub-study, obtain respective samples for biomarkers (see Section 9.7.8.1.2) and/or for iohexol clearance (see Section 9.7.8.1.3), perform echocardiography (see Section 9.7.8.1.1)
- Assess if the subject has any endpoint event(s) (see Table 13–1 and Section 9.6.1.3.1)
 - Any eGFR declines that meet endpoint criteria that are identified at the EOS Visit, or that cannot be confirmed by the time of the EOS Visit, should be confirmed 4 weeks after the initial decline

- In exceptional circumstances only, if the subject is unable to attend this visit during the given timeframe, the subject (or primary physician/ next of kin) should be contacted to obtain survival status.
- Record adverse events (see Section 9.6.1), accounting for the rules of assessment and documentation (see Section 9.6.1.3).

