9.6.1.3.1 Event versus outcome

The efficacy and pre-defined disease-related outcome events specified in Figure 9–1 will not be documented as (S)AEs. Instead, these events will be documented only on the Outcome Event pages of the eCRF. In addition, they will not be reported as SAEs and will neither be unblinded, nor reported to regulatory authorities, IECs, or investigators (see also Section 9.6.1.4 for details).

However, they will be collected in the eCRF, monitored by the DMC during the study and analyzed in the clinical report after study termination. If unexpected safety issues are identified, specific amendments will be implemented.

Figure 9–1 Medical finding during the study: event versus outcome

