9.6.1.4 Reporting of serious adverse events (SAEs) - amended

This section was changed in Amendment 3, see Section 15.1.2.30.

The definition of SAEs is provided in Section 9.6.1.1. Each SAE must be followed up until resolution or stabilization by submission of updated reports to the designated recipient.

The pre-defined disease-related efficacy events (see Table 13–1) will not be subject to AE documentation and expedited reporting as SAE because they are not unexpected in this study population. Thus, they will not be recorded as SAEs on the AE page and will not be sent to

Sponsor's Pharmacovigilance department. Instead, these events will be recorded on the eCRF as outcome events. Consequently, they will neither be unblinded, nor reported to regulatory authorities, IECs or investigators. However, they will be collected in the eCRF, evaluated by the CEC, monitored by the independent DMC during the study and analyzed in the clinical study report after termination of the study. The independent DMC will periodically review and assess all safety data for imbalances in safety outcomes. It is believed that in this way, patient safety can continue to be monitored throughout the duration of the trial, without affecting the integrity of the study. Should unexpected safety issues be identified, specific amendments will be implemented.

All other SAEs that fulfill the seriousness criteria provided in Section 9.6.1.1 must be collected on the AE page of the eCRF and reported as SAEs to the Sponsor's Pharmacovigilance department. All SAEs that fulfill SUSAR criteria as defined by the ICH E2A Guideline will be reported to the concerned authorities by expedited means (see details below).

The investigator is responsible for continuing to follow-up on all SAE reports (whether or not the event is related to study drug) until resolution of the event, or until the event is considered chronic and/or stable by the investigator and/or other physician who is responsible for the subject's medical care. Follow-up SAE reports will be reported according to the same timelines as initial reports, as soon as new significant information becomes available.

Investigator's notification of the sponsor

All investigators will be thoroughly instructed and trained on all relevant aspects of the investigator's reporting obligations for SAEs. This information, including all relevant contact details, will be summarized in the investigator site file and updated as needed.

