6.2.3.6 Outcome events reported by the investigators

Outcome events using the investigator-reported terms will be summarized by treatment group, using tables analogous to those for adverse events. No statistical testing of these events will be performed, as the adjudicated outcome events are components of the primary, secondary and exploratory efficacy variables.

An overall summary of all outcome events will be generated by treatment group.

The number of subjects with all outcome events, outcome events from randomization up to 30 days after stop of study medication, post-treatment outcome events occurring more than 30 days after stop of study drug or after the EOS Visit, outcome events by maximum intensity and outcome events by worst outcome will be summarized by treatment group using MedDRA terms grouped by Primary System Organ Class and Preferred Term.

The incidence rate of outcome events per 100 patient-years will also be provided by treatment group using MedDRA terms grouped by Primary System Organ Class and Preferred Term. The time under risk for the incidence rates is defined as the time from randomization until the first onset of the event or the last date of contact with the subject in case no such event is recorded.

Outcome events will be listed separately in the section 14.2 tables.

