6.4.1 Adverse events

Adverse events (AEs) will be coded using the Medical Dictionary for Regulatory Activities (MedDRA, latest version available prior to data base freeze). A listing will be provided linking the original investigator terms and the coded terms. AEs will also be presented grouped by SMQs.

AEs that started or worsened after the first dose of study drug up to 3 days after any temporary or permanent interruption of study drug will be considered as treatment-emergent AEs (TEAEs).

An overall summary of all AEs and TEAEs will be generated by treatment group.

The number of subjects with TEAEs, pre-randomization AEs, post-treatment AEs occurring more than 3 days after any temporary or permanent stop of study drug, treatment-emergent SAEs, treatment-emergent study drug-related AEs, treatment-emergent study drug-related SAEs, treatment-emergent SAEs and TEAEs causing permanent discontinuation of study drug, treatment-emergent non-serious AEs, non-serious AEs, TEAEs by maximum intensity, treatment-emergent SAEs by maximum intensity, drug-related TEAEs by maximum intensity, TEAEs by worst outcome and treatment-emergent SAEs by worst outcome will be summarized by treatment group using MedDRA terms grouped by Primary System Organ Class and Preferred Term.

To comply with local regulatory requirements in Japan, some cardiovascular disease-related outcome events will also be documented as (S)AEs in Japan. These will be included in the outcome event tables (see section 6.2.3.6), and to avoid double-counting of such events, they will not be included in the adverse event summary tables or listings. A separate listing will be generated for all AEs excluded from the AE analysis due to double reporting in Japan.

In case of events with different intensity within a subject, the maximum reported intensity will be used. If intensity is missing, the event will be considered as severe. If the same event is considered as both unrelated and related to the study drug within a subject, the event will be reported as related to study drug. If the drug relationship is missing, the event will be considered as being related to the study drug.

These further safety variables are listed in section 10.3.4 of the protocol:

- Number of subjects with hospitalization for hyperkalemia
- Number of subjects discontinuing study drug permanently due to hyperkalemia
- Number of subjects with hospitalization for worsening of renal function

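### The Post-Treatment Visit has an AE item but no endpoint item, so outcome events after drug is stopped at EOS are captured only indirectly, although the SAP tabulates them by arm

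*Protocol*

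**What the plan says.** - **PT Visit (Protocol 9.2.11).** "The following will be performed at the PT Visit": concomitant medication and adverse events, by telephone. The on-site version for the iohexol sub-study adds only the iohexol sample. The AE item reads "Record adverse events (see Section 9.6.1), accounting for the rules of assessment and documentation (see Section 9.6.1.3".
- **Earlier visits.** The EOS list in 9.2.10 includes "Assess if the subject has any endpoint event(s" as a separate item beside the AE item. Every visit list from Visit 2 onwards does the same.
- **Table 9-1 (Protocol 9.1).** The row "Endpoint assessment ^e" is marked from Visit 2 to EOS, including the Up-titration and PD Visits, and is blank at PT. The AE row is marked at PT.
- **Where outcome events are recorded.** Protocol 9.6.1.3.1 says that "these events will be documented only on the Outcome Event pages of the eCRF", and 9.6.1.4 that "they will not be recorded as SAEs on the AE page". SAP 6.4.1 gives a partial exception: "some cardiovascular disease-related outcome events will also be documented as (S)AEs in Japan".
- **What is reported.** SAP 6.2.3.6 summarizes investigator-reported outcome events by treatment group. One category runs from randomization to 30 days after stopping drug. Another is "post-treatment outcome events occurring more than 30 days after stop of study drug or after the EOS Visit". For the incidence rates, time at risk runs to the first event or to the last contact with the subject. No testing is planned.

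**The concern.** For subjects still on drug at EOS, PT is the only planned contact after the drug is withdrawn. It asks directly about ordinary AEs but not about the cardiovascular and renal outcomes that the trial studies, and those outcomes may not be entered on the form that the call does complete. Subjects who stop early keep an explicit endpoint item at their later scheduled contacts.

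At stake are the post-treatment rows of the SAP 6.2.3.6 tables. If some clinical events between EOS and PT go unreported, event counts after withdrawal are too low, while the interval still adds time at risk. No confirmatory result is at stake.

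**Working it through.** The plan gives no figure for this point, so there is none to reproduce. The check compares the texts and then sizes the window.

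**1. Is the omission consistent?** Yes. Both versions of the PT list lack the endpoint item, and the Table 9-1 endpoint row agrees. The Amendment 4 rationale also describes the call as covering AEs and concomitant medication.

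**2. What happens to a myocardial infarction reported at PT?** The AE item operates under Protocol 9.6.1.3, which uses open questioning. The AE definition in 9.6.1.1 is broad enough to cover the event. Subsection 9.6.1.3.1 then sends it to the Outcome Event pages. The AE observation period lasts until the last follow-up visit, which for these subjects is PT (Protocol section 5, Follow-up Period), and no text closes the Outcome Event pages at EOS. A route therefore exists, but it needs the subject to volunteer the event and the site to follow a cross-reference.

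**3. What happens to a new eGFR-based event?** It cannot be seen, because PT has no laboratory sample for creatinine. Only declines already found by EOS are confirmed afterwards (9.2.10).

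**4. How does the SAP use the window?** Read literally, an event 10 days after stopping at EOS falls in both SAP categories. An event 10 days after an early stop, before EOS, falls only in the first. The post-treatment row therefore starts at EOS for EOS stoppers and at day 31 for early stoppers. For EOS stoppers who take the PT call, last contact is normally that call, so the interval counts as time at risk.

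**5. How many events occur in the window?** Inputs:
- N = 5800 randomized (SAP section 3).
- Window of 28-33 days (4 weeks + 5 days).
- Upper on-drug share: from 5% annual discontinuation and 11-44 months of follow-up (Protocol 10.4), the mean of exp(-0.05t) for t uniform on 0.917-3.667 years is (0.9552 - 0.8325)/(0.05 × 2.75) = 0.89. This applies the finerenone discontinuation rate to both arms.
- Lower on-drug share: 0.65, assumed.
- CV composite rate: 5-10% a year, assumed.

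Patient-years = N × share × days/365.25:
- Low: 5800 × 0.65 × 28/365.25 = 289; × 0.05 ≈ 14 events.
- High: 5800 × 0.89 × 33/365.25 = 466; × 0.10 ≈ 47 events.

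A second set of assumptions uses N × share × (1 - exp(-h × days/365.25)) with h = -ln(1 - annual rate):
- 4800 subjects, 70% on drug, 5%, 28 days: 13.2 events.
- 5800 subjects, 100% on drug, 12%, 33 days: 66.6 events.

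The 12% is the assumed placebo rate for the primary renal composite. Part of that composite is eGFR-based and invisible at PT, so the upper figure overstates what a question could find.

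**6. Effect on the overall incidence rates.** Mean planned follow-up is (11 + 44)/2 = 27.5 months, or 27.5/12 × 365.25 = 837 days. The window adds 28/837 = 3.3% to 33/837 = 3.9% to it. Even if every event in the window were missed and everyone were on drug at EOS, a roughly constant overall rate would be understated by only about 3-4%. Any distortion lies mainly in the post-EOS row.

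**The case against.** The strongest reply is that keeping events off the AE pages is a filing rule and does not stop the site from asking. Step 2 bears this out. A reader might infer that the events are solicited by neither route; the documents do not support that. Protocol 13.1.2 also tells sites to report any suspected endpoint to the CEC, and a SAP category for events after EOS shows that the sponsor expects some to arrive.

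A blank endpoint row at PT may also seem natural, since its Table 9-1 footnote concerns eGFR confirmation and PT has no laboratory sample. But the endpoint item in the visit lists refers to Table 13-1, which includes myocardial infarction, stroke, heart-failure hospitalization and death. If open AE questioning were enough for these, the separate item at every earlier post-randomization visit would be unnecessary.

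A reader might also infer that coverage of the first four weeks off drug is complete for early stoppers and nil for EOS stoppers. That is not established. The PD Visit is dropped if it cannot be held within 7 days (9.2.9). Under the protocol section on discontinuation of study drug, later contacts are four-monthly and need not be in person. The fair contrast is a direct prompt, often retrospective, against an open AE question.

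It also stands that the tables are descriptive, that the trial is double-blind and gives no reason to expect different ascertainment by arm, and that the protocol has no drug-withdrawal objective.

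**Conclusion.** The concern holds in a limited form. PT is the only visit after Visit 1 with an AE item and no endpoint item. For subjects who stop at EOS, clinical outcome events in the next four weeks are captured indirectly, while SAP 6.2.3.6 tabulates that period by arm. The tables may under-report; the direction is toward too few events and the amount is unknown.

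A reader might take the 14-47 events as lost, or conclude that follow-up cannot show a rise after withdrawal or makes withdrawal look safer than it is. The documents support none of these. The figure is the number expected to occur in both arms together, it rests on an assumed CV rate and on-drug share, and nothing in the documents gives the fraction missed.

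The primary and secondary time-to-event analyses close at EOS (SAP 6.2.1.1 and 6.2.2.1) and are unaffected. The list of exempt events is taken from Table 13-1, to which Protocol 9.6.1.4 refers. This is a cheap improvement to a scheduled procedure and does not threaten the trial's conclusions.

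**What to change.** 1. Add the item "Assess if the subject has any endpoint event(s" to both versions of the PT list in Protocol 9.2.11, and mark the PT column of the Table 9-1 endpoint row.
2. State there that clinical outcome events found at PT go on the Outcome Event pages. They stay outside the primary and secondary analyses. New eGFR-based events are not covered, because no sample is taken.
3. In SAP 6.2.3.6, show post-EOS outcome events by arm, separately for subjects who stopped drug at EOS and those who stopped earlier.

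The cost is one extra question at a contact already scheduled and a few extra outcome forms. The protocol already accepts telephone enquiry about endpoints for subjects who cannot attend (6.4.1.1 and 9.1). If the protocol cannot be changed, add a note beside the SAP 6.2.3.6 tables that events between EOS and PT were ascertained only through the AE question.

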9.3 Population characteristics

9.3.1 Demographic

The following demographic data will be collected in the eCRF:

- Year of birth and age at the Run-in Visit
- Ethnic group
- Race
- Sex
- Smoking habits and alcohol consumption.

9.3.2 Medical history - amended

This section was changed in Amendment 3, see Section 15.1.2.24.

Medical history findings (i.e. previous diagnoses, diseases or surgeries) meeting all criteria listed below will be collected as available to the investigator:

- Pertaining to the study indication or CVD history
- Start before randomization
- Considered relevant to the study (e.g. CV and metabolic diseases, periodontal disease)
- Medical history related to concomitant medication.

Detailed instructions on the differentiation between (1) medical history and (2) adverse events can be found in Section 9.6.1.1.

9.4 Efficacy- amended

This section was changed in Amendment 3, see Section 15.1.2.25.

The parameters in Section 9.4.1 (primary), Section 9.4.2 (secondary) and Section 9.4.3 (exploratory) will be used to assess the efficacy of the study drug.

Efficacy endpoints will be evaluated by a Clinical Event Committee (CEC) (see Section 13.1.2).

Kidney failure is defined as either the occurrence of ESRD or an eGFR of less than 15 mL/min/1.73 m², confirmed by a second measurement at the earliest 4 weeks after the initial measurement. ESRD is defined as the initiation of chronic dialysis (haemo- or peritoneal-dialysis) for at least 90 days or renal transplantation. In addition, the eGFR threshold of 15 mL/min/1.73 m² is consistent with the definition of kidney failure from KDIGO (Kidney Disease: Improving Global Outcomes)(3) and was chosen in order to include an objective component to the endpoint because the decision to initiate dialysis therapy or kidney transplantation may be affected by factors other than the eGFR. All other definitions of individual endpoints (e.g. CV death) will be provided in the Endpoint Manual.

9.4.1 Primary efficacy variable

The primary efficacy variable will be the time to the first occurrence of the composite endpoint of onset of kidney failure, a sustained decrease of eGFR \geq 40% from baseline over at least 4 weeks, or renal death.

9.4.2 Secondary efficacy variables

Secondary efficacy variables will be as follows:

- Time to first occurrence of the following composite endpoint: cardiovascular (CV) death or non-fatal CV events (i.e. non-fatal myocardial infarction, non-fatal stroke, or hospitalization for HF)
- Time to all-cause mortality
- Time to all-cause hospitalization

- Change in UACR from baseline to Month 4
- Time to the first occurrence of the following composite endpoint: onset of kidney failure, a sustained decrease of eGFR $\geq 57\%$ from baseline over at least 4 weeks, or renal death.

9.4.3 Other exploratory efficacy variables - *amended*

This section was changed in Amendment 3, see Section 15.1.2.26.

Other exploratory efficacy variables will be as follows:

- Time to onset of ESRD
- Time to onset of eGFR decrease of $\geq 40\%$ from baseline sustained over at least 4 weeks
- Time to onset of eGFR decrease of $\geq 57\%$ from baseline sustained over at least 4 weeks
- Time to CV death
- Time to first CV hospitalization
- Time to first non-fatal CV event (e.g. myocardial infarction, stroke, hospitalization for HF)
- Number of subjects with new diagnosis of atrial fibrillation or atrial flutter
- Number of subjects with new diagnosis of HF
- Change in UACR from baseline
- Change in eGFR from baseline
- Regression from very high to high albuminuria and high albuminuria to albuminuria accompanied by a decrease in UACR of at least 30% from baseline
- Number of subjects with UACR decrease of at least 30% from baseline at any time post-baseline
- Number of subjects with UACR decrease of at least 50% from baseline at any time post-baseline
- Change in QoL summary scores measured by the following health-related quality of life (HRQoL) questionnaires: Kidney Disease Quality of Life (KDQOL-36) and EuroQol Group 5-dimension, 5-level questionnaire (EQ-5D-5L), see Section 9.7.7 for details.

